The NCEH laboratory will perform the analyses of serum PFAS according to the biochemical analytical plan (Attachment 2) and approved laboratory methods (Kuklenyik 2015). The NCEH laboratory staff will also aliquot and ship blood and serum specimens to participating laboratories for the analyses of the effect biomarkers according to the plan. The recipient will store the urine samples and conduct analyses at a later date when more knowledge is gained about urinary PFAS and effect biomarkers and until the laboratory methods are developed. Residual blood and urines will be archived at NCEH so that additional PFAS or effect biomarkers can be analyzed as new knowledge and analytical methods become available.

23 3.6.5 Questionnaire

Each adult participant, and a parent of the child participant, will complete a questionnaire during theappointment for the blood draw.

26 3.6.5.1 Children and Parents

27 Study staff will request that the parents of the child participant complete the questionnaire. The 28 questionnaire will obtain demographic information (e.g., education, primary occupation), residential history, water consumption habits, medical history of the mother and child, the child's medications, the mother's reproductive history (including maternal age at birth of the participating child) and any occupational exposures the mother may have had to PFAS. The questionnaire will be administered in two formats: a form for the child whose parent is not also a participant (Attachment 15), and an abbreviated form for the child whose parent is also an adult participant (Attachment 15a).

6 The questionnaire will obtain the mother's and child's residential history in the study area, and the dates 7 and length of time of the pregnancy and breastfeeding of the child. The questionnaire will also obtain 8 information on the water consumption habits (including use of water for formula, juices, etc., bottled 9 water use) of the mother and child when they resided in the study area. Information on the mother's 10 workplaces in the study area (location and dates) and the child's daycare and schools in the study area 11 (location and dates) will be obtained.

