12 The questionnaire will request information on the child's height and weight, vaccination history, and 13 whether the child regularly exercises, currently smokes (and the number of cigarettes/day), or consumes 14 alcohol (and the number of drinks/week). The questionnaire will ask when the female child first began to 15 menstruate. The questionnaire will include specific questions addressing health outcomes of interest. 16 For example, for ADHD, the questionnaire will ask, "Has a doctor or health professional ever told your 17 child that your child has/had ADD or ADHD?" If the answer is "yes," a second question will ask for a list of 18 medications the child took for the condition. The questionnaire will ask if the child had learning or 19 behavioral problems, and if so, the type of problem and the treatment used. Questions would be included 20 for the hypersensitivity-related outcomes, asthma, atopic dermatitis (or atopic eczema), and allergies. The 21 study will attempt to confirm diseases and conditions reported in the questionnaire by accessing medical 22 records sending abstraction forms (Attachments 17&17a) to the medical care provider identified by the 23 participants on their consent forms (Attachment 7b5).

24 3.6.5.1.1 Child/Parent Neurobehavioral Assessments

25 **Table 3** provides the neurobehavioral test battery for children enrolled in the Multi-site Study.

26 Trained professionals will administer the following tests to children:

The Wechsler Abbreviated Scale of Intelligence – 2nd Edition (WASI – II) test will be administered
 to measure Full Scale IQ (FSIQ) among children 6-17 years (15 minutes). Intelligence testing of
 children aged 4 – 5 years will not be conducted.

- Each child 4-16 years will complete the NEPSY-II selected tests. Except for Theory of Mind, these
 additional tests are short and useful to assess memory and inhibition. For all the NEPSY II tests,
 children 4 years would take about 52 minutes, and children ≥5 years, about 70 minutes.
- Children aged 4 7 years will complete the Connors Kiddie Continuous Performance Test (K-CPT
- 5
- 2) (8 minutes), and children aged >7 years will complete the Connors CPT 3 (14 minutes).
- 6 Trained professionals will administer the following tests to parents about their children:
- Strengths and Difficulties Questionnaire (SDQ) (5 minutes).

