Attachment 8.

Thank you so much. To get you prepared for the appointment, I have just one more question about some medicines [you/your child/both you and your child] might be taking now.

- Are [you/your child/either you or your child] taking any medication for diabetes?
 - YES > Because [you/your child/both you and your child] take diabetes medication, we want to give special instructions about your appointment(s). We will be mailing out a reminder card. If [you/your child/both you and your child] can fast and take your medication without eating, please do. If [you/your child/both you and your child] cannot fast, please eat, and take your medications as usual. Please eat only fat-free or low-fat food, if possible. Please write down the time and the foods you eat. You may drink water during this time. [GO TO CLOSING REMARKS]
 - NO > Please remember not to eat for at least 8 hours before your appointment. You may drink water during this time. We also want to remind you to collect your urine sample(s) that morning and bring it. We will be mailing out a reminder card. [GO TO CLOSING REMARKS]

[CLOSING REMARKS FOR OFFICE VISIT] Don't forget to bring all your medications with you to your appointment. [For children – Don't forget to note the dates of (his/her) vaccinations. We will be asking about that.] Please let us know as soon as possible if you have to cancel your appointment. You can call at [STUDY TELEPHONE NUMBER] if you have to cancel your appointment. Thank you for being part of our study.

[CLOSING REMARKS FOR HOME VISIT] Don't forget to gather all your medications for your appointment. [For children – Don't forget to note the dates of (his/her) vaccinations. We will be asking about that.] Please let us know as soon as possible if you have to cancel your appointment. You can call at [STUDY TELEPHONE NUMBER] if you have to cancel your appointment. Thank you for being part of our study.

Note: This script cannot be used as a voicemail message.

Multi-site Study Appointment tracking form

Adult Study ID No.	Order	Drder		Completed		Clinic or In-field	
 Child Study ID No. 	Assigned by Coordinator	Comments	Date mm/dd/yy	Time hh:mm	0 cl 1 ha	'inic ome	
Informed Consent	1.		_ _ / _ _ / _ _	AM _ _ : _ PM	0	1	
Update Contact Information	2.		_ _ / _ _ / _ _	AM _ _ : _ PM	0	1	
Blood Draw/ Urine Collection	[]		_ _ / _ _ / _ _	AM _ _ : _ PM	0	1	
Assess Current Medication	[]		_ _ / _ _ / _ _	AM _ _ : _ PM	0	1	

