Section F: Child's Medical History

F1. Have you ever been told by a doctor or other health care provider that your child has or had any of the following medical conditions? Fill out the table below. Circle appropriate response and ask the respondent to specify as directed.

м	edical condition		If yes, what year was your child diagnosed?
-		Yes (Please specify)	year
a. Ca	ancer?	No Don't know	
b. All	lergies?	Yes (Please specify) No Don't know	year
c. At	copic dermatitis/eczema?	Yes (Please specify) No Don't know	year
d. As	sthma?	Yes No Don't know	year
e. Ch (rł	nronic stuffy/runny nose hinitis/sinusitis)?	Yes No Don't know	year
f. Hi	gh cholesterol?	Yes No Don't know	year
g. Th	nyroid disease?	Yes (Please specify) No Don't know	year
h. De	elayed puberty?	Yes (Please specify) No Don't know	year
i. Ot	besity?	Yes No Don't know	year
j. Lu	ipus	Yes No Don't know	year
k. Ce	eliac disease	Yes No Don't know	year
l. Cr	ohn's disease	Yes No Don't know	year
m. Di	abetes	Yes, Type 1 Yes, Type 2 Yes, Type unknown No Don't know	year

	Medical condition		If yes, what year was your child diagnosed?
n.	Scleroderma	Yes No Don't know	year
0.	Attention deficit hyperactivity disorder (ADHD) or attention deficit disorder (ADD)?	Yes No → go to p Don't know → go to p	year
p.	How is your child treated for ADHD or ADD?		year
q.	Other learning or behavioral problems?	Yes (Please specify) No \rightarrow go to Question F2. Don't know \rightarrow go to Question F2.	year
r.	How is your child treated for their learning or behavioral problems?		

F2. What age was your child last vaccinated for:

Diphtheria, Tetanus, Pertussis ("DTaP")	age	Don't know	never was vaccinated
"Tdap" booster Tetanus, Diptheria, Pertussis	age	Don't know	never was vaccinated
Measles, Mumps, Rubella ("MMR")	age	Don't know	never was vaccinated
Tetanus shot (for a puncture wound or cut)	age	Don't know	never was vaccinated

FOR GIRLS ONLY

F3. Has your daughter ever used an oral contraceptive ("birth control pill")?

- ____Yes
- ___No \rightarrow go to Question F5
- ____Don't know \rightarrow go to Question F5
- ____Refused to answer \rightarrow go to Question F5

F4. When did your daughter last use an oral contraceptive ("birth control pill")?

___ Month/Year

F5. At what age did your daughter begin menstruation (have her first period)?

___Age

- ____Has not yet begun to menstruate \rightarrow go to Section G
- ____Don't know
- F6. Does your daughter's period occur regularly (every month)?

____Yes

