Attachment 15a. Multi-site Study Child Questionnaire — Short Form

(best completed by the child's birth mother who is also an adult participant)

Form Approved OMB No. 0923-XXXX Exp. Date xx/xx/201x

ATSDR estimates the average public reporting burden for this collection of information as 15 minutes per response, including the time for reviewing instructions, searching existing data/information sources, gathering and maintaining the data/information needed, and completing and reviewing the collection of information. An agency may not conduct or sponsor, and a person is not required to respond to a collection of information unless it displays a currently valid OMB Control Number. Send comments regarding this burden estimate or any other aspect of this collection of information, including suggestions for reducing this burden to CDC/ATSDR Information Collection Review Office, [name]; ATTN: PRA (0923-xxxx).

Adult Study ID No.	(alias)
Parent Study ID No.	
Child Study ID No.	

Section A: Demographic Information

A1. What is your relationship to your child?

____Birth mother

____Birth father

____Adoptive mother

____Adoptive father

____Legal guardian

____Other relationship: specify _____

____Refused to answer

A2. What is your child's sex?

____Male

____Female

____Refused to answer

A3. What is your child's date of birth?

__(MM/DD/YYYY)

____Refused to answer

A4. Do you consider your child to be Hispanic or Latino?

____Yes

____No

____Refused to answer

A5. What race do you consider your child to be? Mark all that apply.

____American Indian or Alaska Native

____Asian

- ____Black or African American
- ____Native Hawaiian or Other Pacific Islander
- ____White
- ____Refused to answer
- A6. What is the highest grade level of education your child has completed? ____grade
- A.7 What is the highest level of education you completed?
- Less than high school
- ____Some high school
- ____High school graduate or equivalent (GED)
- ____Some university/college
- ____Technical or trade school
- ____University/college graduate
- ____Graduate school or higher
- A8. What is the child's household income (from all sources)?
- ____Less than \$25,000
- ____\$25,000 to \$69,000
- ____\$70,000 to \$149,000
- ____More than \$150,000
- ____Don't know
- ____Refused to answer

A9. During the last 12 months did the child have any kind of health insurance?

- ___Yes
- ___No
- ____Don't know
- ____Refused

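### The child questionnaires lack items that Section 3.6.5.1 says they collect, and its short-form rule conflicts with the form headers, so maternal history is left out when the father is the only participating parent

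*Protocol*

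**What the plan says.** Section 3.6.5.1 (Children and Parents) sets out what the child questionnaire will obtain. On lifestyle, it will ask "whether the child regularly exercises, currently smokes (and the number of cigarettes/day), or consumes" "alcohol (and the number of drinks/week"). On the mother, it will obtain her "reproductive history (including maternal age at birth of the participating child"), her residences and workplaces in the study area, and the dates and length of the pregnancy and of breastfeeding. On water, it will obtain "information on the water consumption habits (including use of water for formula, juices, etc., bottled" water use, for both mother and child.

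The same section defines two formats: Attachment 15 for a child whose parent is not a participant, and an "abbreviated form for the child whose parent is also an adult participant (Attachment 15a"). The header of Attachment 15a describes it as best completed by the child's "birth mother who is also an adult participant". The header of Attachment 15 is written for the birth mother who is not one.

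Section 3.9 builds each participant's cumulative serum level partly from questionnaire data, including breastfeeding, parity and blood donation. Section 3.10 makes the estimated cumulative level the exposure of the primary analyses and selects confounders by a 10% change-in-estimate criterion.

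**The concern.** There are two separate mismatches. The first is between the text and the instruments: if the forms are used as printed, several variables that the protocol commits to will not be in the data set. A change-in-estimate criterion can be applied only to measured covariates, so exercise, smoking and alcohol could not be tested for any child outcome. Those outcomes include lipids, obesity, ALT and GGT among the child hypotheses in Section 2.5.2. Infant formula and bottled water bear directly on how much contaminated water the child took in.

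The second is between the routing rule and the form headers. The short form makes sense when the mother answers her own adult questionnaire. Section 3.6.5.1 triggers it on any participating parent. If that parent is the father, the questions about the mother are dropped, and nothing in the protocol asks for them elsewhere. Under Section 3.2.1 a child can qualify solely through exposure before birth or through breast milk, and for such a child the mother's history is the exposure history.

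**Working it through.** No arithmetic is at issue. The check sets the text beside the instruments. The lettered sections of both forms run without a gap (A to H in Attachment 15, A to G in Attachment 15a), so lost pages do not explain what is absent.

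**Step 1. Items stated in 3.6.5.1 against the forms**

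| Stated in 3.6.5.1 | Attachment 15 | Attachment 15a | Available another way? |
|---|---|---|---|
| Exercise | no item | no item | no |
| Cigarettes per day | no item | no item | no |
| Drinks per week | no item | no item | no |
| Bottled water | no item | no item | no |
| Formula | no item of its own; at most implied in B2 and B7 (cups of tap water or of drinks made with it) | no item of its own; at most implied in B1 | partly |
| Maternal age at birth | no age or birth date | no age or birth date | only if the birth mother is an adult participant |

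For the last row, the adult contact block in Attachment 4 takes a date of birth and item A3 takes the child's, so the difference gives maternal age. The parent contact block takes no date of birth, so this does not work for long-form children. The child medical-record form (17b) and school-record form (18b) do not carry the missing items.

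On formula, the residence tables ask one average tap-water intake per address. For a child who has stayed at one address since birth, that single figure mixes infancy with later childhood.

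**Step 2. Which form a child gets**

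| Adult participant in the household | Rule in 3.6.5.1 | Form headers |
|---|---|---|
| Birth mother | 15a | 15a |
| Neither parent | 15 | 15 |
| Father only | 15a | 15 |

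The two sources disagree only in the last row.

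**Step 3. What changes in that row**

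| Maternal information | Attachment 15 | Attachment 15a |
|---|---|---|
| Residences | B4–B9 | not asked (B2 covers the child only) |
| Jobs | D1–D3 | not asked (Section D covers the child only) |
| Transfusion and blood donation | C1–C2, C5–C7 | not asked |
| Pregnancy dates, breastfeeding duration and stop date | Section G | not asked |
| Tap water in pregnancy and breastfeeding | B10–B11 | B3–B4, kept |

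Four blocks drop out and one is kept. Three of the four (residences, workplaces, pregnancy and breastfeeding dates) are promised by name in 3.6.5.1, so the routing rule defeats its own section. Blood donation is among the inputs listed in Section 3.9.

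**The case against.** Several points on the other side have force.

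- **The headers and the screening script lean towards the birth mother.** Attachment 4 says it is best if she enrols, and staff who follow the headers would give a father-only household the long form. That stands, but it is a preference. The only stated rule is the one in 3.6.5.1, and it says parent.
- **A reader might infer that all maternal exposure data vanish in father-only households.** The documents do not support this. Attachment 15a keeps B3–B4, including an answer for not having breastfed, and every address of the child. The birth date roughly dates the pregnancy, and the screening script asks for every child whether the mother was a firefighter, trained with the foam or worked in PFAS manufacturing. The father's own residential history may serve as a proxy if the parents lived together, although the protocol does not provide for that.
- **A reader might infer that nothing can be recovered after the visit.** That is also too strong. Attachment 10 foresees further contact for clarifying questions and collects three tracing contacts, both child forms offer a follow-up call to the birth mother, and Section 3.8.4 provides for resolving missing values. However, the call can complete only the items on the form in use, and recontacting families for late recall is a poor substitute for a few questions at the visit.
- **A reader might add vaccination timing to the list,** since parents are told "to note the dates of (his/her) vaccinations. We will be asking about that" while the form asks "F2. What age was your child last vaccinated for". This is not a defect. Age at last vaccination, with the birth date and the blood-draw date, gives approximate time since vaccination, and 3.6.5.1 promises only a vaccination history.
- **Section 3.10 plans bias analysis for unmeasured risk factors.** That helps with what cannot be measured; it does not replace items the protocol has already decided to collect.
- **The forms are drafts,** with placeholder OMB numbers. This limits the seriousness and makes the correction cheap.

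**Conclusion.** The point holds as a mismatch between the protocol text and its own instruments. Of six items named in 3.6.5.1, four (exercise, smoking, alcohol, bottled water) are on neither form, formula is at most implied, and maternal age is derivable only when the birth mother is an adult participant. This applies to the child forms as a whole, hence to all of the planned 2,000 or more children, although smoking and alcohol matter mainly for the older ones. Separately, the routing rule and the headers conflict for father-only households, and the rule as written drops four blocks of maternal history there.

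The number of children in such households cannot be estimated from the protocol, which gives no share, and no count should be attached to the point. The conclusion assumes that the forms are used as printed and the rule as written. The adult questionnaire (Attachment 16) is not in the text reviewed; the conclusion also assumes that a father's copy would not contain the mother's history. That exercise, smoking and alcohol could confound the child analyses is a subject-matter judgement. The inconsistency stands without it, because the protocol itself says they will be collected.

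**What to change.** Before the forms are finalised:

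1. Add to both Attachments 15 and 15a: exercise, cigarettes per day and drinks per week (age-gated), formula mixed with tap water, bottled-water use, and the mother's date of birth. If the sponsor decides against any of these, delete it from 3.6.5.1 and give the reason.
2. Reword 3.6.5.1 so that Attachment 15a is used only when the birth mother is the adult participant, and Attachment 15 in every other case, including when the father is the only participating parent. This brings the rule into line with the headers.

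The cost is a few extra minutes per interview and the longer form for father-only households. The change is easiest now, while the forms carry placeholder OMB numbers and Attachment 5c lists IRB and OMB approvals as pending.

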Behavior Rating Inventory of Executive Function [®] – Preschool Version (BRIEF [®] -P)	Executive Function - Preschool	4-5	Parent about Child	10 minutes

1

For each child, the recipient will also review and abstract school records, including special education records, to identify learning problems and behavioral problems (Attachment 18b). If the parent reports that the child has a developmental disability (e.g., ADHD, autism, or a learning disability), then the recipient shall obtain and abstract the special education records for the child including the individualized education program (IEP), the IEP evaluation report ("Full Individual Evaluation" or "FIE"), and if available, the Independent Educational Evaluation.

8 3.6.5.2 Adults

9 Each adult participant will complete a questionnaire requesting demographic information, residential 10 history, water consumption habits, occupational history, medical history and reproductive history (Attachment 16). In particular, the questionnaire will ask if the participant ever had kidney disease, liver 11 12 disease, cardiovascular disease, hypertension, high cholesterol, thyroid disease, diabetes, autoimmune 13 diseases, osteoporosis, osteoarthritis, pregnancy-induced hypertension, infertility, and endometriosis. 14 For each reported disease or condition, the questionnaire will ask about the date of diagnosis, the medical 15 provider who made the diagnosis, and the medications used for treatment the questionnaire will ask the 16 participant about conditions that might affect PFAS serum levels such as date of menopause, menstrual

- 1 cycle information, blood transfusions, and blood donations. The study will attempt to confirm diseases
- 2 and conditions reported in the questionnaire by medical records review (Attachments 17&17a).

3 3.6.6 Exit Procedures

At the end of the data collection, study coordinators or staff will review recorded items in the participant's
Appointment Tracking Form for completeness (Attachment 9).

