6 The adult participant or the parent of the child participant will receive a copy of the participant's Body 7 and Blood Pressure Measures Report (Attachment 19). These results will be immediately available and 8 will require no further evaluation or interpretation with two exceptions. The adult participant or the 9 parent of the child participant will receive a supplemental notice if the participant has a critical blood 10 pressure measure (diastolic blood pressure > 120 mm Hg, or systolic blood pressure >180 mm Hg). In this 11 case, a Critical Hypertension Notice will be appended to the Body and Blood Pressure Measurements Report along with written and verbal recommendations to obtain immediate medical attention. If the 12 participant does not have a personal physician, the study coordinator will provide a referral. If the 13 participant has an elevated but non-critical blood pressure measure (resting blood pressure > 140/90), an 14 15 Elevated Hypertension Notice will be appended to the Body and Blood Pressure Measures Report with written and verbal recommendations to obtain clinical follow-up. 16

- 17 3.6.6.1 Gift Cards as a Token of Appreciation for Participation
- 18 As a token of thanks for participation, the recipient will offer gift cards according to the following schedule:
- \$25 for body and blood pressure measures, and for blood and urine collection;
- 20 \$25 for completed questionnaire; and
- \$25 for child/parent completion of the neurobehavioral test battery
- Trained study staff will document provision of gift cards on the hard copy form (**Attachment 9**). As part of the exit procedures, the participant will sign this form to document receiving the gift card.

24 3.6.7 Adverse Events

The risks associated with this study are minimal. There is a small chance of unexpected or adverse events
 occurring during the course of this project. Unanticipated problems involving risk to the subjects or others

will be reported to the CDC Human Institutional Review Board (IRB) in accordance with institutional
 policies and procedures.

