Attachment 13.

BLOOD PRESSURE

Blood Pressure:	
1. / (mm Hg)	Modification to Procedure?
	□ Yes □ No
2. / (mm Hg)	Reason:

3. |__|_|/|__|_| (mm Hg)

This chart reflects blood pressure categories defined by the American Heart Association. *Defined by American Heart Association

Check	BP Category	Systolic BP		Diastolic BP	Action*
One		(mm Hg)		(mm Hg)	
	Normal	<120	and	<80	No referral
	Elevated	120-129	or	<80	No referral
	Hypertension (Stage 1)	130-139	or	80-89	See a physician within 2 months
	Hypertension (Stage 2)	≥ 140	or	≥ 90	See a physician within 1 month
	Hypertensive Crisis	> 180	or	> 120	See physician immediately
CI					

Classification of BP in Adults Aged 18 Years or Older.

* If systolic and diastolic categories are different, the shorter recommended time for recheck and referral takes precedence. If two or three repeated systolic or diastolic measurements are abnormal but fall in different categories, determine the appropriate category based on their average.

If referral made, to whom (mark one):

No referral made
Emergency Room (Phone: xxx-xxx)
Participant's Provider (Name: _______; Phone: ______; Phone: ______);
Referral 3 (Phone: xxx-xxx)
Referral 4 (Phone: xxx-xxx)

Agency for Toxic Substances and Disease Registry

HUMAN HEALTH EFFECTS OF DRINKING WATER EXPOSURES TO PER- AND POLY-FLUOROALKYL SUBSTANCES (PFAS): A MULTI-SITE CROSS-SECTIONAL STUDY

"Multi-site Study"

Manual of Procedures

[DATE]

(PLACEHOLDER: this manual is under development)

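### For readings from 130 or 80 up to 140/90, Section 3.6.6 and Attachments 13 and 19 disagree on whether a blood-pressure notice is due, and children are reported in adult bands

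*Protocol*

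**What the plan says.** Three current texts of the protocol govern the same reading.

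- **Section 3.6.6 (Exit Procedures).** Each adult, or the parent of each child, leaves with the Attachment 19 report, and the results are said to need no further interpretation apart from two cases. The first is a critical reading ("diastolic blood pressure > 120 mm Hg, or systolic blood pressure >180 mm Hg"), which adds a notice and urgent referral. The second applies when the "participant has an elevated but non-critical blood pressure measure (resting blood pressure > 140/90"), which adds a notice with written and verbal advice to seek follow-up. Children are included without any age condition: the adult or the "parent of the child participant will receive a supplemental notice if the participant has a critical blood" pressure reading.
- **Attachment 13 (measurement form).** Stage 1 (130–139 or 80–89) carries the action "See a physician within 2 months". Stage 2 (from 140 or from 90) means referral within 1 month, and the crisis row says "See physician immediately". If the two values fall in different categories, the shorter time applies. The form takes an adult or a child study number, but the chart is captioned "Classification of BP in Adults Aged 18 Years or Older".
- **Attachment 19 (report handed out).** It uses the same Stage 1 and Stage 2 cut points. One hypertension notice covers both stages: it calls the pressure very high and asks the participant to arrange an appointment. The nurse must mark a category before the participant leaves. The list of attachments shows no child version.

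**The concern.** Staff complete Attachment 13, hand over Attachment 19 and follow 3.6.6 for the same person on the same day. If the texts set different triggers, whether someone receives an appended notice and is told face to face to seek follow-up depends on which text the staff member has in mind. The study plans for about six recipients, so practice could differ between sites. The vocabulary adds to the risk: 3.6.6 calls readings above 140/90 elevated, while both attachments use that word for 120–129, with no referral.

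The children's problem is separate. The protocol labels its own action chart as adult, yet a child's reading is judged against the 3.6.6 limits and marked in the same Stage 1 and 2 bands on a sheet given to the parent. A parent could be falsely reassured or needlessly alarmed. Elsewhere the protocol does separate the ages: Attachment 21 has child columns, for example for lipids.

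What is at stake is the consistency of safety advice. No analysis depends on these rules.

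**Working it through.** No planned figure needs reproducing; the check is whether three written rules agree. Let S be systolic and D diastolic, in mm Hg.

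**Rules for prompting follow-up or more**

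- 3.6.6: S > 140 or D > 90. The text writes 140/90 without saying whether either value or both must exceed the limit; either is assumed here.
- Attachment 13: S ≥ 130 or D ≥ 80.
- Attachment 19: S ≥ 130 or D ≥ 80.

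**Where they differ.** The attachments prompt action and 3.6.6 does not exactly when (S ≥ 130 or D ≥ 80) and S ≤ 140 and D ≤ 90.

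**Check along each axis.** With D fixed at 70, the three texts differ on follow-up at each integer S from 130 to 140. With S fixed at 110, they differ at each integer D from 80 to 90. The only other differences are at exactly 180 and exactly 120, and those depend on how a sign is read (below).

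| Reading | 3.6.6 | Attachment 13 | Attachment 19 | Same prompt? |
|---|---|---|---|---|
| 125/75 | none | no referral | no notice | yes |
| 135/85 | none | 2 months | Stage 1 notice | no |
| 140/90 | none | 1 month | Stage 2 notice | no |
| 160/85 | non-critical notice | 1 month | Stage 2 notice | yes |
| 135/95 | non-critical notice | 1 month | Stage 2 notice | yes |
| 160/100 | non-critical notice | 1 month | Stage 2 notice | yes |
| 181/110 | critical notice | immediate | crisis notice | yes |

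The rows 160/85 and 135/95 show why the condition that neither value exceeds 140/90 is needed: one value in the 130–140 or 80–90 range is not enough.

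**Sensitivity to the reading of 140/90.** If both values had to exceed the limit, 160/85 would also get no notice under 3.6.6. The conflict would widen, not shrink.

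**Exactly 180 or 120.** Section 3.6.6 and Attachment 19 both use a strict sign. Attachment 13's crisis row prints an underlined >.

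- Read as ≥, a reading of 180/110 is immediate on Attachment 13 but non-critical in the other two.
- Read as a plain >, 180/110 is Stage 2 there too, and nothing conflicts.

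The Stage 2 row of the same table prints an underlined true ≥, so underlining alone does not settle which is meant.

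**Elevated row.** Both attachments join 120–129 and below 80 with *or*. A reading of 115/70 is Normal (below 120 and below 80) and also meets Elevated through D < 80. Neither category leads to referral, so no action changes.

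**Children.** Attachment 19 does not label its bands as adult. That they are adult bands is inferred from its Stage 1 and 2 cut points, which match the chart Attachment 13 captions for ages 18 and over. Nothing in Attachment 19 or in 3.6.6 gives a different limit for ages 4–17.

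**The case against.** The strongest reply is that nobody in the disputed range goes without advice. A reader might infer that 3.6.6 leaves a participant at 135/85 uninformed, and the documents do not support that: 3.6.6 itself hands out Attachment 19, whose printed text tells that participant to call a doctor. That is compatible with Attachment 13's 2 months. This stands, and it limits the point to whether the appended notice and the verbal recommendation are due.

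A reader might also infer a firm conflict at exactly 180 or 120. That rests on taking an underlined > as ≥, which is plausible but not established, and it concerns only averaged readings that land exactly on a limit.

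A third inference is that Attachment 19's crisis text, which tells the participant that they cannot go on with the study, contradicts 3.6.6, which only refers. No contradiction is shown. Section 3.6.4 puts blood pressure before the blood draw when the two are consecutive, so a crisis reading can occur mid-visit and a stop may be a sensible safeguard. The Manual of Procedures is marked "PLACEHOLDER: this manual is under development", and the consent pages are not in the text available, so a supporting rule may exist there.

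Finally, the forms are visibly unfinished and the measurements are stated to be for research, not diagnosis. That keeps the point minor. It does not remove it: Attachments 13 and 19 carry no note that their blood-pressure bands will change, and a later manual would still leave contradictory forms in use.

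**Conclusion.** Two defects hold.

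1. When systolic is 130–140 or diastolic 80–90 and neither value exceeds 140/90, 3.6.6 calls for no notice or verbal recommendation, while Attachment 13 refers (within 2 months, or within 1 month at exactly 140 or 90) and Attachment 19 prints a hypertension notice. This does not depend on the sign at 180 and 120, and it would only widen if 140/90 required both values to be exceeded.
2. Participants aged 4–17 must be marked in bands whose Stage 1 and 2 cut points the protocol elsewhere captions as adult, with no child version of the report. On the stated goal this concerns the reports of at least 2,000 children. It rests on the shared cut points, because Attachment 19 itself carries no age label.

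The documents give no distribution of readings, so the number falling in the disputed range cannot be stated. This is a minor participant-safety consistency correction, worth making before field use, with no effect on power, error rates or estimates.

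**What to change.** - **One trigger.** Set the non-critical trigger in 3.6.6 to systolic ≥ 130 or diastolic ≥ 80, with Attachment 13's referral times. Alternatively, move both attachments to a single clinician-approved trigger. Either way, state explicitly whether one value or both must reach the limit.
- **Children.** Do not mark participants under 18 in the adult bands. Give them a child version of the report, with limits chosen by a clinician; the documents supply none.
- **While editing.** Print one explicit sign at 180 and 120 in all three texts. Change *or* to *and* in the Elevated row of both attachments; this is wording only and changes no action.
- **Leave alone.** Keep the crisis sentence about not continuing, since removing it could take away a safety stop.

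The cost is edits to one section and two forms, plus one child version of the report, before field use. Data collection, sample size and analysis are unchanged.
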